6.3 PATIENT SETS ANALYSED

The following two analysis sets are defined as in CTP Section 7.3. The safety set will be the basis of all demographic, baseline and safety analyses. Efficacy analysis will be on basis of the efficacy set.

[figure not shown]
- Safety set:
This patient set includes all patients who had no invalid registration, who were dispensed Trazenta® and were documented to have taken at least one dose of Trazenta®. Patients with CRF data which were not ensured by the investigator will be excluded from this patient set.

[figure not shown]
Proprietary confidential information © 2017 Boehringer Ingelheim International GmbH or one or more of its affiliated companies

[figure not shown]
- **Efficacy set:**
This patient set includes all patients with Trazenta[®] in the safety set who have at least one available on-treatment HbA1c value.

Additional analysis set is defined for comparing the baseline date between Trazenta[®] group and other group:

- **Baseline set:**
This patient set includes all patients who had no iPV leading to exclude from baseline set (i.e., category “Baseline”).

6.5 POOLING OF CENTRES

This section is not applicable because centre is not included in the statistical model.

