## POST MARKETING SURVEILLANCE STUDY PROTOCOL SYNOPSIS

Name of company/Marketing Authorisation Holder: Boehringer Ingelheim		Tabulated Study Protocol	
Name of finished product: Trazenta ® Tablets			
Name of active ingredient: Linagliptin			
Protocol date 3 July 2012	Trial number 1218.95		Revision date: 4 April 2013
Title of study:	Post Marketing Surveillance study on Long term Drug Use of Trazenta ® Tablets in Patients with type 2 Diabetes Mellitus		
Co-ordinating Investigator:	Not applicable		
Study sites :	400 <del>600</del>		
Clinical phase:	IV		
Objectives:	To investigate the safety and efficacy of long-term daily use of Trazenta ® Tablets as monotherapy in patients with type 2 diabetes mellitus. To assess baseline characteristics of patients with type 2 diabetes mellitus starting Trazenta ® Tablets or any other oral antidiabetic monotherapy (naïve or switched from prior therapy of different oral antidiabetic drug) .		
Methodology:	Non-interventional, prospective, observational		
No. of patients:	Total entered: 3,000 <del>6,000</del> each treatment: Trazenta ® Tablets: 1,500 <del>3,000</del> Oral antidiabetic drugs except Trazenta ® Tablets: 1,500 <del>3,000</del>		
Diagnosis:	Type 2 diabetes mellitus		
Main criteria for inclusion:	Trazenta ® Tablets: Male and female patients with type 2 diabetes mellitus who have never been treated with Trazenta ® Tablets/ linagliptin ( monotherapy ) before enrollment. Other oral antidiabetic drug: Male and female patients with type 2 diabetes mellitus starting any other oral antidiabetic monotherapy (naïve and switch) except Trazenta ® Tablets.		
Test product :	Trazenta ® Tablets		
dose:	5 mg		
mode of admin. :	Oral		
Comparator product:	Oral antidiabetic drugs except Trazenta ® Tablets		

Proprietary confidential information.

© 2013 Boehringer Ingelheim International GmbH or one or more of its affiliated companies. All rights reserved.

This document may not - in full or in part - be passed on, reproduced, published or otherwise used without prior written permission.

Name of company/Marketing Authorisation Holder: Boehringer Ingelheim		Tabulated Study Protocol	

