**Proprietary confidential information.**

© 2013 Boehringer Ingelheim International GmbH or one or more of its affiliated companies. All rights reserved.

This document may not - in full or in part - be passed on, reproduced, published or otherwise used without prior written permission.

Other oral antidiabetic drug:

Planned number of patients to be entered is **1,500** ~~3,000~~.

After the enrolment of each patient for whom Trazenta® Tablets are prescribed, the patient immediately following and initiating any other oral antidiabetic drug should be enrolled. The total number of Trazenta® Tablets patients and comparators are the same at each site.

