## 7.6 DETERMINATION OF SAMPLE SIZE

The sample size was determined based on the following: To detect an ADR with an incidence of 0.20-1% (or 0.310-16%) or greater in at least one patient with a probability of 95% (or 99%) or greater, at least 1,500 3,000 patients need to be entered and have at least one observation after treatment.

[REDACTED]

Proprietary confidential information.

© 2013 Boehringer Ingelheim International GmbH or one or more of its affiliated companies. All rights reserved.

This document may not - in full or in part - be passed on, reproduced, published or otherwise used without prior written permission.

[REDACTED]

[REDACTED]

[REDACTED]

[REDACTED]

[REDACTED]

[REDACTED]

[REDACTED]

All patients within renal and hepatic dysfunction will be assessed.

If the number of patients is less than expected numbers, registration period or sample size will be extended.

Other oral antidiabetic drug:

Descriptive statistics for all baseline characteristics will be analyzed.

As this will be exploratory and descriptive and no statistical tests will be performed the same number of patients for both groups is appropriate.

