6.2 IMPORTANT PROTOCOL VIOLATIONS

The following table defines the different categories of important protocol violations (PVs). The right-most column describes which PVs will be used to exclude patients from the different patient analysis sets. The final decision about which patients will be excluded from analysis sets will be taken during the course of the study and at report planning meetings before database lock at the latest.

Table 6.2: 1 Important protocol violations

Category/ Code	Description	Example/Comment	Excluded from
A	Entrance criteria not met		
A1.1	No type 2 diabetes		Efficacy / Baseline
A1.2	Patient received Trazenta [®] treatment before registration	This rule will apply for the patients with Trazenta [®]	Efficacy / Safety / Baseline
A1.3	Patient not treated as mono therapy at baseline	1) Used antidiabetic medication but stopped after start of TRZ 2) Used antidiabetic medication and continued after start of TRZ 3) Used antidiabetic medication and changed to non TRZ at start of TRZ 4) No antidiabetic medication until start of TRZ, but start antidiabetic medication with TRZ	Efficacy / Safety / Baseline
A1.4	Registered as other OAD but Trazenta [®]	This rule will apply for the patients with OAD	Baseline
B	Informed consent		
C	Trial medication and randomisation		
C1	Incorrect study medication taken		

Table 6.2: 1(continued) Important protocol violations

Category/ Code	Description	Example/Comment	Excluded from
C1	Incorrect study medication taken		
C1.1	No treatment with Trazenta®	This rule will apply for the patients with Trazenta®	Efficacy / Safety / Baseline
E	Missing data		
E1	No baseline value	No available baseline value of HbA1c for efficacy analysis This rule will apply for the patients with Trazenta®	Efficacy
G	Trial specific		
G	G1	Invalid registration	
G1.1	No patient visit after entry	Patient made no visit after the entry This rule will apply for the patients with Trazenta®	Efficacy / Safety / Baseline
G1.2	Multiple registration	Patient who were already registered this trial with another patient ID In this case, all data for the later patient will not be used.	Efficacy / Safety / Baseline
G1.3	Registration rule not followed		Efficacy / Safety / Baseline
G1.4	Patient started Trazenta® treatment without registration period	This rule will apply for the patients with Trazenta®	Efficacy / Safety / Baseline
G1.5	Not continuous investigation		Efficacy / Safety / Baseline

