7.5 SECONDARY ENDPOINT(S)

For the change from baseline in HbA1c at the last observation, descriptive statistics will be calculated. A 95% confidence interval for the mean change from baseline will also be calculated.

[REDACTED]

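### The SAP leaves site out of the HbA1c interval and the baseline ASD although patients enter in site clusters; the likely effect is small and cheap to allow for

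*SAP*

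**What the plan says.** **Clustering.** The protocol synopsis plans 400 sites and 3,000 patients, 1,500 in each group. Protocol 3.3 has each investigator enrol consecutive starters. After each Trazenta patient, the next patient starting another oral antidiabetic is enrolled, so that the numbers of Trazenta "patients and comparators are the same at each site".

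**HbA1c interval.** SAP 7.5 states: "A 95% confidence interval for the mean change from baseline will also be calculated". It names no variance estimator. SAP 6.5 sets site aside: "This section is not applicable because centre is not included in the statistical model". The natural reading is the ordinary one-sample interval.

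**Baseline comparison.** SAP 7.1 computes an ASD between the two groups from pooled means or proportions and flags values above 0.1. The baseline set (SAP 6.3) drops individual patients according to SAP Table 6.2: 1:
- Limited to Trazenta: A1.2, C1.1, G1.1 and G1.4. The comments under A1.3 (not on monotherapy at baseline) are also written around the start of Trazenta.
- Limited to comparators: A1.4, "Registered as other OAD but Trazenta".
- Not limited to one group: A1.1, G1.2, G1.3 and G1.5.

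No rule removes the paired patient or rebalances a site after an exclusion.

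**The concern.** There are two separate points.

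First, patients treated at one site share prescribers and local habits, including when other antidiabetic therapy is added, which Protocol 4.2 does not restrict. If their HbA1c changes are positively correlated, 1,500 patients carry less information than 1,500 independent ones, and the planned interval covers the true mean less often than 95%.

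Second, one-for-one enrolment gives both groups the same mix of sites while both are complete. If exclusions take more Trazenta patients from some sites than from others, the two groups no longer weight the sites alike. A difference between sites can then appear in the pooled ASD as a difference between drug groups. Describing such differences is one of the study's aims (Protocol 2.1 and 2.2).

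**Working it through.** **The plan's own figure.** Protocol 7.6, read with the struck-out values removed, bases 1,500 Trazenta patients on seeing at least one case of a reaction with incidence 0.2% (probability 95%) or 0.31% (99%). With P = 1 − (1 − p)^n: 1 − 0.998^1500 = 0.9504 and 1 − 0.9969^1500 = 0.9905. Solving for n gives 1,497 and 1,484. The figure reproduces and is not in dispute.

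**Cluster size.** 1,500/400 = 3.75 Trazenta patients per site. Protocol 3.3 gives 5 to 10 patients per site under its Trazenta heading, but 1,500 at 5 to 10 per site needs 300 to 150 sites, not 400. Counting both groups, 3,000/400 = 7.5 fits. An upper limit of 10 for both groups together means 5 Trazenta patients, so 3.75 and 5 are shown.

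**HbA1c interval.** Design effect DEFF = 1 + (m − 1) × ICC. The width factor is √DEFF, and the coverage of the planned interval is 2Φ(1.96/√DEFF) − 1. The ICC values are assumptions.

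| m | ICC | DEFF | Correct interval wider by | Coverage of planned interval |
|---|---|---|---|---|
| 3.75 | 0.01 | 1.028 | 1.4% | 94.7% |
| 3.75 | 0.05 | 1.137 | 6.7% | 93.4% |
| 3.75 | 0.10 | 1.275 | 12.9% | 91.7% |
| 5 | 0.01 | 1.040 | 2.0% | 94.5% |
| 5 | 0.05 | 1.200 | 9.5% | 92.6% |
| 5 | 0.10 | 1.400 | 18.3% | 90.2% |

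The documents give no SD for HbA1c change. With an assumed SD of 1.0 point and n = 1,500, the planned half-width is 1.96/√1500 = 0.0506. At 3.75 per site it becomes 0.0513 (ICC 0.01) to 0.0571 (ICC 0.10).

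**Site mix in the ASD.** Let site means have SD √ICC in units of the patient SD, with comparators complete. The shift is √ICC times the difference between the site effect averaged over the retained Trazenta patients and the plain average over sites. This was simulated with 400 sites, 4 Trazenta patients each, 10% to 30% of Trazenta patients excluded, and site-specific exclusion rates (SD 1 on the logit scale) correlated with the site mean. All these settings are assumptions. The last column is the analytic extreme in which the top-ranked sites lose all their Trazenta patients: √ICC × φ(z)/(1 − f), where f is the fraction excluded and z the (1 − f) normal quantile.

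| ICC | Excluded | Correlation 0 | 0.5 | 1 | Whole sites lost |
|---|---|---|---|---|---|
| 0.02 | 10% | 0.001 | 0.006 | 0.012 | 0.028 |
| 0.02 | 30% | 0.002 | 0.017 | 0.034 | 0.070 |
| 0.05 | 10% | 0.002 | 0.010 | 0.019 | 0.044 |
| 0.05 | 30% | 0.004 | 0.027 | 0.054 | 0.111 |
| 0.10 | 20% | 0.004 | 0.026 | 0.051 | 0.111 |
| 0.10 | 30% | 0.005 | 0.038 | 0.075 | 0.157 |

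**A strong contrast.** Suppose hospitals and clinics enrol equally, 40% of Trazenta patients are excluded at hospitals and 5% at clinics, and a trait is present in 50% and 10% of patients respectively. Trazenta prevalence is (0.60 × 0.50 + 0.95 × 0.10)/1.55 = 0.255, against 0.30 in comparators. The ASD is 0.101 with no difference within any site. This requires 22.5% of Trazenta patients to be excluded and a between-site variance share of 0.04/0.21 = 0.19, nearly twice the largest ICC used above.

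**The case against.** The strongest reply is that little depends on this. Protocol 7.2 calls the analyses descriptive and disclaims formal inference, HbA1c is a secondary endpoint in a safety surveillance, and a half-width change of about 0.006 point alters no conclusion. That stands as a limit on importance. It does not make a reported 95% interval cover 95%, and it does not explain what an ASD above 0.1 reflects.

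Local laboratories are also a weak source of correlation here: the endpoint is a change from baseline, so a constant laboratory offset cancels within the patient. That stands too, and leaves shared prescribing and case mix as the likelier sources.

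Several stronger readings are tempting but unsupported:
- *The one-for-one enrolment makes the interval too narrow.* The interval uses Trazenta patients only. Any effect comes from clustering of those patients.
- *The interval is known to be too narrow, by up to 38%.* No ICC is given. The 38% needs 10 Trazenta patients per site and an ICC of 0.10; 10 at each of 400 sites would be 4,000 patients, not 1,500.
- *The exclusions bias the pooled ASD.* Unequal losses alone do not. Exclusion rates must vary by site and relate to the site mean. C1.1 and A1.4 also remove patients whose drug does not match their registered group, which is a correction.
- *The enrolment rule was meant to remove site differences.* The protocol gives no such purpose. Protocol 7.6 justifies equal numbers only by the exploratory, descriptive nature of the comparison.

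SAP 6.4, 7.6 and parts of 7.5 and 7.8.1 are redacted, so any model there was not seen. SAP 6.5 nevertheless says that centre is not included.

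**Conclusion.** The point holds as a minor one. The HbA1c interval ignores clustering and is anticonservative under any positive site correlation: about 1% to 13% too narrow relative to its planned width at 3.75 Trazenta patients per site, or 2% to 18% at 5, for assumed ICCs of 0.01 to 0.10. These figures take equal site sizes. In HbA1c points the loss is small.

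The baseline ASD may carry site differences, because exclusions fall mostly on one group and no rule restores site balance. Under the simulated settings the mean shift is at most 0.005 when exclusion is unrelated to the site mean, and at most 0.075 at full correlation. It passes 0.1 only under strong contrasts, such as the loss of whole sites or the hospital and clinic example. Exclusion rates and their link to site are not in the documents, so whether this occurs can be judged only from the data.

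**What to change.** Replace SAP 6.5 with a statement that covers both analyses.

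1. **HbA1c.** Compute the SAP 7.5 interval with a site-clustered (sandwich) variance. The point estimate is unchanged.
2. **Baseline.** Beside the pooled ASD, report a site-stratified one: the within-site differences averaged with weights n1 × n2/(n1 + n2), in absolute value, divided by the same SD as in SAP 7.1. When n1 = n2 at every site the weights are n1/2, and the result equals the pooled ASD. A gap between the two therefore shows the effect of lost site balance, including any sites that dropped out.
3. **Counts.** Tabulate patients per site and group after exclusions, and state whether the 5 to 10 per site in Protocol 3.3 counts both groups.

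The site name is already captured at registration (Protocol 6.2.1), so the cost is a few lines of code. The interval will probably be slightly wider. Sites left with one group drop out of the stratified ASD, and these may be the sites most affected by exclusions, which is why the counts are needed. The stratified ASD does not correct patient-level selection caused by the exclusions themselves.

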6.6 HANDLING OF MISSING DATA AND OUTLIERS

Missing or incomplete AE dates are imputed according to BI standards (see “Handling of Missing and Incomplete AE Dates”). (2)

No imputation will be performed in efficacy and safety analyses.

Missing or partial date information will be replaced according to following rules.

YEAR	MONTH	DAY	YMD	DT
“Unknown” (tick-box)			UNKNOWN	.
<2007	Null	Null	2007	2007/07/01
yyyy	Null or “Unknown”	Null	yyyy	yyyy/07/01
yyyy	mm	Null or “Unknown”	yyyymm	yyyy/mm/15
yyyy	mm	“First ten days of the month”	yyyymm “First ten days of the month”	yyyy/mm/01
yyyy	mm	“Second ten days of the month”	yyyymm “Second ten days of the month”	yyyy/mm/11
yyyy	mm	“Third ten days of the month”	yyyymm “Third ten days of the month”	yyyy/mm/21

If the date of data which is collected as after treatment of Trazenta[®] in the CRF is before start of Trazenta[®], The will be missing.

6.7 BASELINE, TIME WINDOWS AND CALCULATED VISITS

With regard to efficacy and safety endpoints, the term “baseline” refers to the last observed measurement prior to administration of Trazenta[®].

Efficacy analyses will be performed based on calculated visits as shown in [Table 6.7: 1](#). If two or more data points of a patient fall into the same interval, closest value to the planned day will be selected. If there are two observations which have the same difference in days to the planned day or if there are two observations on the same day, the first value will be used.

Table 6.7: 1 Baseline, time windows and calculated visits

Week label	Planned days	Time window (actual days on treatment)	
		Start	End
Baseline	0	NA	1
Week 12	84	2	133
Week 26	182	134	231
Week 40	280	232	322
Week 52	364	323	406
Week 64	448	407	497
Week 78	546	498	637
Week 104	728	638	819
Week 130	910	820	1001
Week 156/EOT	1092	1002	End of study

7. PLANNED ANALYSIS

For End-Of-Text tables, the set of summary statistics is: N / Mean / SD / Min / Median / Max.

For tables that are provided for endpoints with some extreme data, median, quartiles and percentiles should be preferred to mean, standard deviation, minimum and maximum

Tabulations of frequencies for categorical data will include all possible categories and will display the number of observations in a category as well as the percentage (%) relative to the respective treatment group (unless otherwise specified, all patients in the respective patient set whether they have non-missing values or not). Percentages will be rounded to two decimal place. The category missing will be displayed only if there are actually missing values.

7.1 DEMOGRAPHIC AND OTHER BASELINE CHARACTERISTICS

Descriptive statistics for the demographic and other baseline characteristics described in [Section 5.4](#) are planned by treatment groups (Trazenta[®] or others). Absolute standard difference (ASD) will be also calculated based on the following formulas. (1)

For binary variable:

$$ASD = \left| \frac{(\hat{p}_{TRZ} - \hat{p}_{OAD})}{\sqrt{\frac{\hat{p}_{TRZ}(1 - \hat{p}_{TRZ}) + \hat{p}_{OAD}(1 - \hat{p}_{OAD})}{2}}} \right|$$

For continuous variable:

$$ASD = \left| \frac{(\bar{x}_{TRZ} - \bar{x}_{OAD})}{\sqrt{\frac{s_{TRZ}^2 + s_{OAD}^2}{2}}} \right|$$

ASD > 0.1 is considered to be statistically meaningful difference.

7.2 CONCOMITANT DISEASES AND MEDICATION

Concomitant diseases will be coded by the latest version of Medical Dictionary for Regulatory Activities (MedDRA). Frequency of patients will be summarised by treatment (Trazenta[®] or others), SOC and PT.

Concomitant medication will be coded by latest version of “Nihon-iyakuhinshu”.

7.3 TREATMENT COMPLIANCE

It is not planned the analysis for the treatment compliance.

7.4 PRIMARY ENDPOINT(S)

There is no primary endpoint for efficacy as the primary objective of the PMS study is the evaluation of safety.

7.5 SECONDARY ENDPOINT(S)

For the change from baseline in HbA1c at the last observation, descriptive statistics will be calculated. A 95% confidence interval for the mean change from baseline will also be calculated.

[REDACTED]

7.7 EXTENT OF EXPOSURE

Only descriptive statistics are planned for this section of the report. The followings are the categories of exposure-ranges (in weeks):

- >0 to 12 weeks, >12 to 26 weeks, >26 to 40 weeks, >40 to 52 weeks, >52 to 64 weeks,
- >64 to 78 weeks, >78 to 104 weeks,>104 to 130 weeks,>130 to 156 weeks, >156 weeks

7.8 SAFETY ANALYSIS

7.8.1 Adverse events

Unless otherwise specified, the analyses of adverse events (AEs) will be descriptive in nature. All analyses of AEs will be based on the number of patients with AEs and NOT on the number of AEs.

Furthermore, for analysis of AE attributes such as duration, severity, etc. multiple AE occurrence data on the case report form, will be collapsed into AE episodes provided that all of the following applies:

- The same MedDRA lowest level term was reported for the occurrences
- The occurrences were time-overlapping or time-adjacent (time-adjacency of 2 occurrences is given if the second occurrence started on the same day or on the day after the end of the first occurrence)
- Treatment did not change between the onset of the occurrences OR treatment changed between the onset of the occurrences, but no deterioration was observed for the later occurrence

For further details on summarization of AE data, please refer to the guideline 'Analysis and Presentation of Adverse Event Data from Clinical Trials' ([3](#)).

AE analyses will be carried out after integrating AE data from CRF and AE data from perceive system.

In addition, AEs coded as “no adverse event” will not be included in the AE analyses.

An overall summary of adverse events will be presented. This will be also made for patients who added patients not treated as mono therapy at baseline to safety set (i.e. all patients with Trazenta® treatment).

The frequency of patients with ADRs, with serious AEs, with AEs leading to discontinuation, and with AEs leading to death will be summarised by treatment, primary SOC and PT. AEs and ADRs will also be reported by intensity.

To compare risks of overall ADR in different patient subgroups, frequency tabulation stratified by different patient subgroups will be provided with odds ratios and exact 95% confidence intervals whenever specified (see [Section 6.4](#)). Logistic regression will be used for odds ratio.

In addition, summaries for the time to onset of first episode for the ADRs will be tabulated, by duration (>0 to 12 weeks, >12 to 26 weeks, >26 to 40 weeks, >40 to 52 weeks, >52 to 64 weeks, >64 to 78 weeks, >78 to 104 weeks, >104 to 130 weeks, >130 to 156 weeks, >156 weeks), by treatment, primary SOC, and PT.

An ADR is defined as an AE for which either the investigator or the sponsor (or both) assess the causal relationship to Trazenta® either as “Related,” “Probably related,” or “Cannot be

denied”. The SOC’s will be sorted according to the standard sort order specified by European medicines agency, PTs will be sorted by frequency (within SOC).

[REDACTED]

[REDACTED]

[REDACTED]

[REDACTED]

[REDACTED]

[REDACTED]

- [REDACTED]
- [REDACTED]
- [REDACTED]
- [REDACTED]
- [REDACTED]

[REDACTED]

[REDACTED]

- [REDACTED]
- [REDACTED]
- [REDACTED]
- [REDACTED]
- [REDACTED]
- [REDACTED]

[REDACTED]

[REDACTED]

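### The supportive adverse event summary in SAP 7.8.1 is described as covering all Trazenta-treated patients, but its stated rule restores only the non-monotherapy exclusions

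*SAP*

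**What the plan says.** SAP 6.3 states: "The safety set will be the basis of all demographic, baseline and safety analyses". The definition begins: "This patient set includes all patients who had no invalid registration, who were dispensed Trazenta", and it requires at least one documented dose. It ends with a further condition: "Patients with CRF data which were not ensured by the investigator will be excluded from this patient set".

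Table 6.2: 1 in SAP 6.2 lists the violations that remove a patient from Safety: A1.2, A1.3, C1.1 and G1.1 to G1.5. Two of these have only a bare description and no comment: G1.3, "Registration rule not followed", and G1.5, "Not continuous investigation". Final exclusions are decided as the study proceeds, and before database lock at the latest.

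SAP 7.8.1 plans one wider population, for the overall summary of adverse events only. It adds "patients not treated as mono therapy at baseline to safety set (i.e. all patients with" Trazenta treatment, so the parenthesis equates the result with everyone treated. The tables by system organ class and preferred term are not repeated in it.

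**The concern.** One sentence gives a construction rule and a description that would be equivalent only if A1.3 were the sole code taking dosed patients out of Safety. It is not. A programmer who follows the rule produces a table that does not contain everyone its description claims. One who follows the description has to override the rule.

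This matters more here than in most descriptive studies. Safety is the primary objective, and the sample size rests on seeing at least one case of a rare reaction, so single cases count. The study is unrandomised, and the protocol has adverse events transmitted as they occur. Exclusions can therefore be decided when a patient's outcome is already known. G1.5 concerns departures from consecutive enrolment, where selection could be related to outcome. A summary that really covered every treated patient would let a reader see whether the exclusions changed the picture. One that only claims to cover them gives false reassurance.

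**Working it through.** **Step 1: compare the sets.** Inputs are Table 6.2: 1, the safety set definition in SAP 6.3 and the construction rule in SAP 7.8.1.

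| Reason for removal from Safety | Patient dosed? | Restored by adding A1.3? |
|---|---|---|
| A1.2, Trazenta before registration | Yes, by definition | No |
| A1.3, not monotherapy at baseline | Yes | Yes |
| C1.1, never treated | No | Not relevant |
| G1.1, no visit after entry | Possibly | No |
| G1.2, duplicate registration | Person stays under the first ID; only the later record goes | Not relevant |
| G1.3, registration rule | Possibly | No |
| G1.4, treatment started without registration period | Yes, by definition | No |
| G1.5, not consecutive | Possibly | No |
| CRF not confirmed (SAP 6.3) | Possibly | No |

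Safety set plus A1.3 therefore equals all treated patients only if no dosed patient falls in any row marked No. A single such patient breaks the equality.

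**Step 2: compare the codes with protocol 3.3.** The protocol prefers registration within 14 days, counting the day of first administration, and keeps later registrants in the safety and efficacy analyses. Registration after the first dose is therefore normal. Read literally, A1.2 would catch patients whom the protocol enrols as intended. G1.3, and possibly G1.4, could catch late registrants whom it keeps. The SAP does not say how these codes are limited.

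**Step 3: reproduce the plan's own figure.** Protocol 7.6 shows old and new values run together. Removing the superseded 0.1% and 0.16% leaves 0.2% with 95% probability, 0.31% with 99%, and 1,500 patients.

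P(at least one case) = 1 − (1 − p)^N

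- p = 0.002, N = 1,500: 1 − 0.998^1500 = 95.04%
- p = 0.0031, N = 1,500: 1 − 0.9969^1500 = 99.05%
- Required N = ln(0.05)/ln(0.998), rounded up to 1,497, and ln(0.01)/ln(0.9969), rounded up to 1,484

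The planned 1,500 is reproduced and is not in dispute. The expected number of cases at 0.2% is 1,500 × 0.002 = 3.

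**Step 4: illustrate the size.** The documents give no count of affected patients, so the shares below are assumptions. The same formula is used, with the same risk in excluded and retained patients.

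| Assumed share of 1,500 | Excluded | Retained | P(≥1 case) in retained, 0.2% | P(≥1 case) in retained, 0.31% | P(≥1 case) among excluded, 0.2% |
|---|---|---|---|---|---|
| 1% | 15 | 1,485 | 94.88% | 99.01% | 2.96% |
| 5% | 75 | 1,425 | 94.23% | 98.80% | 13.94% |
| 10% | 150 | 1,350 | 93.30% | 98.49% | 25.94% |
| 20% | 300 | 1,200 | 90.95% | 97.59% | 45.15% |

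The loss of detection probability is modest. The last column is more relevant: it is the chance that a rare reaction occurred in a patient whom the supportive table says it includes but does not.

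**The case against.** The strongest reply is that the exclusions have a basis in the protocol. Protocol 7.3 removes patients with no observation after enrolment, invalid registration or invalid contract, and the SAP groups the G1 codes under invalid registration. That stands, and it is why the main safety set is not challenged here. It does not cover a supportive table described as everyone treated.

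A second reply is that the parenthesis may mean only that patients are included whatever their monotherapy status, or that it overrides the rule so that nobody is left out. Both readings are possible. The first calls for a different description and the second for a different rule, so the sentence needs correcting either way.

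A reader might go further and infer four things that the documents do not support:

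- **That these patients appear in no adverse event table at all.** Parts of SAP 7.8.1 and all of 6.4 are redacted, and 7.8.1 defers further detail to an internal guideline. Only the readable text can be judged.
- **That whole sites drop out together.** Nothing says the codes are applied by site; SAP 6.2 speaks of excluding patients.
- **That a particular proportion is affected.** No figure is given.
- **That serious events are lost to surveillance.** Protocol 5.2.2.2 and 8.4.1 require immediate reporting of every SAE, and 8.4.2 covers expedited reporting. The gap is in the study tables.

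It is also fair to say that a supportive population removing only never-dosed patients and duplicates would have weaknesses. Patients with no visit after entry enlarge the denominator with little chance of a recorded event, and unconfirmed CRF data are less reliable. The fix has to allow for both.

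**Conclusion.** The point holds as an error of definition. The stated rule in SAP 7.8.1 does not yield the population it claims. The dosed patients left out are those under A1.2, G1.3, G1.4 and G1.5 and those with unconfirmed CRFs; any dosed G1.1 patients are also left out. No readable SAP text plans an adverse event summary for them.

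Its numerical effect is unknown, and small if few patients are affected. The illustrative range of 15 to 300 excluded patients rests on assumed shares of 1% to 20% and on equal risk in excluded and retained patients. The mismatch itself needs no such assumption. The correction is worth making because safety is the primary objective, the exclusions are settled while events are being reported, and the scope of three codes is unclear against protocol 3.3. It gives no reason to change the main safety set or the sample size.

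**What to change.** 1. In SAP 7.8.1, define the supportive population as every registered patient with at least one documented Trazenta dose, counting duplicate registrations once. Show patients with no visit after entry (G1.1) and patients with unconfirmed CRF data in separate rows, so that they do not dilute the rates. Alternatively, keep the present rule and relabel the table as the safety set plus A1.3.
2. Under either option, add a short table by exclusion code: dosed patients excluded, and how many of them had an ADR, an SAE or died.
3. State what A1.2, G1.3 and G1.4 cover, and reconcile them with protocol 3.3, so that patients registered after the first dose are not removed against the protocol.
4. Leave the main safety set unchanged.

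The cost is a revised sentence, clarified code descriptions and one small extra table. The first option also means rerunning a planned summary on a wider population that contains some data of lower quality, which the separate rows make visible. No new data collection is planned in this fix: SAP 7.8.1 already integrates adverse events from the CRF and the safety system.
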